## HUMAN SUBJECTS RESEARCH

### **1. Risks to Subjects**

Drs. [name] (PI), [name], and [name] (Co-Is) are licensed clinical psychologists with ample training and experience conducting clinical trials research among individuals and couples with AUD and IPV. Drs. [name], [name], and [name] as well as the research assistant have all completed the University of Miami computer-based CITI Human Subjects Research Education Course. All research activity, informed consents, and continuing reviews will be reviewed by MUSC's IRB in compliance with 45CFR46 before the research is started. Continuing review will occur annually. Study staff will ensure that all information needed for the continuing review is consistent with IRB requirements.

### **A. Human Subjects Involvement, Characteristics, and Design**

A total of 50 couples (100 individual participants) between the ages of 21 and 70 will be recruited over a 2-year period. Women and members of minority groups will be eligible for participation and we will strive to enroll an equal number of women and men with AUD. Children ages 18-21 are *not* eligible for participation. Study inclusion/exclusion criteria are as follows:

Inclusion criteria

- 1) Any gender identity; any race or ethnicity; any sexual orientation; aged 21-70 years.
- 2) Married, cohabiting, or in a committed relationship for  $\geq 6$  months.
- 3) English fluency and cognitive functioning sufficient to provide informed consent and participate accurately (score  $\geq 26$  on the Mini-Mental Status Exam [MMSE]).
- 4) At least one partner within each dyad must meet DSM-V diagnostic criteria for current AUD (assessed by the QuickSCID) *and* current alcohol use based on TLFB.
- 5) At least one partner within each dyad must endorse  $\geq 1$  instance of IPV with their current partner in the past two years (assessed by the Revised Conflict Tactics Scale [CTS-2]).
- 6) Maintenance of psychotropic medications on a stable dose for at least 4 weeks before study initiation.

Exclusion criteria:

- 1) Meeting DSM-5 criteria for a history of or current psychotic, bipolar, or antisocial personality disorders.
- 2) Meeting DSM-5 diagnostic criteria for moderate or severe drug use disorder (e.g., cannabis). Concurrent mild drug use disorders are acceptable due to the marked co-occurrence in AUD populations. Moderate or severe Nonalcoholic Substance Use Disorder is acceptable if there has been no current substance use in the last 1-2 months.
- 3) Alcohol withdrawal as indicated by CIWA-Ar scores  $>8$ .
- 4) Current suicidal or homicidal ideation and intent.
- 5) Serious cardiovascular health conditions (e.g., pacemaker, cardiac arrhythmia, hypertension) *because the safety of HRV-B has not yet been established in these populations.*
- 6) Treatment on medications such as lithium, methadone, alpha or beta blockers or cholinergic/ anticholinergic medications likely to confound normative cardiovascular responding.
- 7) Current neurologic conditions or history of traumatic brain injury.
- 8) Severe *and* unilateral IPV in the past 6 months.
- 9) Current pregnancy.

**B. Sources of Material**

Materials obtained from human participants will include self-report surveys and structured clinical interviews (assessed in the laboratory and remotely using smartphone application), physiological measurements including heart rate and geolocation using a wearable activity tracker, and urine for drug testing.

**C. Potential Risks**

Confidentiality: Breach of confidentiality is associated with all research that is not anonymous. Realization of this risk could cause negative social or legal consequences. Given that data will be linked to participants' identity between completion of the telephone screening interview and completion of the final assessment, this is an important risk to consider. We believe that the risk is very low, given that most data are collected electronically and all data will be stored securely and separately from identifying data. Several safeguards and procedures for protecting data will be in place (see Adequacy of Protection Against Risks below). All possible efforts to protect participants' privacy and confidentiality will be made throughout the course of the study. Participants will be provided with a written informed consent document which specifies the risks and confidentiality protections and limits of study procedures.

Risks associated with EMA: Risks associated with the EMA portion of the study are minimal and include potential loss of confidentiality (described previously) and the potential for surveys to prompt participants at a time when it is inconvenient or unsafe from them to complete a survey (i.e., while driving). Participants will not only provide

their preferred time window for morning reports, but will also be provided with a time window for completing reports to minimize this risk. They are also informed that some missed sessions are expected and that they are not penalized for a few missed sessions. Participants are asked to sign an agreement stating that they will not complete a session while driving or in any other situation where it is potentially unsafe to do so. The EMA assessments do not provide a method of communicating with research staff in real time. Participants will be informed that study staff will not receive EMA responses in real time and thus it is not a method to communicate directly with the study team or receive assistance. All participants will be provided with a variety of community referrals prior to the start of the EMA component of the project.

Risk for increased IPV due to research participation: *This sample will be recruited specifically based on having AUD and a history of IPV in their current relationship. Thus, participants in this project might have instances of psychological and/or physical IPV during the 28-day study period. However, we estimate the risk of IPV occurring, or IPV increasing in frequency or severity to research participation to be very low.* First, [name] has never had a single incident of aggression occur during an assessment or experimental task (e.g., towards partners, research staff, or others) in a study of alcohol-facilitated IPV, *including a recently completed sample of N=100 couples similar to the proposed one, wherein participants were required to meet diagnostic criteria for AUD and have recent physical IPV in their relationship.* [name] team has also not had increased IPV reported in the context of laboratory trials or ongoing couple therapy trials among couples with AUD. Thus, extensive prior research suggests that the proposed study procedures are safe and the exclusion criteria are effective at minimizing risks of adverse events. Second, in our *recently completed NIAAA-funded laboratory-based studies of couples with AUD and IPV, post-study debriefing have not detected study-induced aggression or relationship conflict.* In a sample of N=100 couple with co-occurring physical IPV and AUD, no instances of increased subjective aggression or actual IPV were reported. [name] previously surveyed IPV investigators nationwide (N=59) to identify the frequency, severity, and type of adverse events (AEs) reported in IPV research. Results indicated a low frequency of AEs, strong agreement among investigators regarding safety precautions, and high efficacy of those methods. These methods, such as private informed consent and assessment apart from one's partner and IPV assessment using validated instruments (CTS-2) will be applied in the current project and AEs will be closely monitored by our team and our DSMB. While the present study does not include an aggression induction or laboratory aggression task, existing literature in the field of alcohol-facilitated IPV suggest that among men (N=400) surveyed immediately after completing a laboratory IPV task, an extremely small proportion (1.8%) reported an increased likelihood of behaving aggressively as a result of participation. Participants denied any specific plans of action and reported one-week later that these feelings did not persist. Rather, they reported that the study made them realize that they could be aggressive and, compared to their prior self-perception of extreme "non-aggressiveness", indicated an increased likelihood of behaving aggressively when provoked in the future. As independent evidence of these results, another research team systematically assessed the post-experiment impact of completing questionnaires, engaging in anger arousing conflict conversations in the laboratory, and being interviewed individually about anger escalation / de-escalation during the conversations among a sample of 85 couples (170 participants) in an intimate partner violence study. In post-experimental interviews, the study was viewed as helpful or neutral by 95.2% of male participants and 96.4% of female participants, both personally and to their relationships. No respondents reported violence as a result of participation. The small number of negative reactions concerned criticisms with particular scales and presumed research hypotheses. Taken together, this evidence indicates that participants' risk of increased aggression as a direct result of study participation is extremely low.

The risk of increased IPV due to study participation is very low primarily because the study team screens out for any severe and/or unilateral IPV at the screening visit. These individuals should not participate in a clinical trial and are referred clinically. This process (referring to higher level of care/clinical provider) is the same for in state and out of state. If the study team becomes aware of increased IPV during the trial, staff will notify the PI, who will consult with the participant(s) privately, thoroughly assess safety and risk and refer clinically. If there is any indication that the study procedures are causing increased IPV, the study procedures will be discontinued immediately and participants will be withdrawn from the study.

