**Participants.** Participants (*50 couples; total N=100 participants; 50% women with AUD*) ages 21-70 years, any gender identity or sexual orientation, and located in any state in the United States. The primary inclusion criteria are that at least one partner within each dyad must: 1) meet DSM-V diagnostic criteria for current AUD (MINI-7) and current alcohol use based on (TLFB), and 2) report at least one instance of physical IPV in the past two years (assessed via the CTS-2). Additional inclusion criteria: 3) Cognitive functioning sufficient to provide informed consent and participate accurately ( $\geq 26$  on the Mini-Mental Status Exam [MMSE]), 4) married, cohabiting, or in a committed relationship for  $\geq 6$  months, and 5) maintenance of psychotropic medications on a stable dose for at least 4 weeks before study initiation (to minimize pharmacologic effects on HRV). Exclusion criteria: 1) History of or current psychotic, bipolar, or antisocial personality disorders, 2) moderate or severe drug use disorder (e.g., cannabis). Concurrent mild drug use disorders are acceptable because of the marked frequency of co-occurrence among individuals with AUD. Moderate or severe Nonalcoholic Substance Use Disorder is acceptable if there has been no current substance use in the last 1-2 months. Drug use will be measured (via urine drug screen, TLFB, and EMA) and controlled for in statistical analyses if needed. 3) Alcohol withdrawal as indicated by CIWA-Ar score  $>8$ , 4) current suicidal or homicidal ideation and intent, 5) serious cardiovascular conditions (e.g., pacemaker, *cardiac arrhythmia, hypertension*) *because the safety of HRV-B has not been established in these populations*, 6) use of medications such as lithium, methadone, alpha or beta blockers or cholinergic/ anticholinergic drugs likely to confound normative cardiovascular responding, 7) current neurologic conditions (i.e., *Parkinson's disease*) or history of traumatic brain injury, 8) severe and unilateral IPV in the past 6 months (for safety), 9) current pregnancy. Pregnancy may cause discrepancies in heart rate that are not attributable to the study intervention which may present a confound for resulting theoretical findings.

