## 2. Adequacy of Protection against Risks

Recruitment and Informed Consent Procedures. All personnel will be trained in the responsible conduct of research. Participants will be recruited from MUSC treatment clinics, community settings, and ads placed on the internet. The screening measure contains questions directly pertaining to the study's inclusion and exclusion criteria. Participants who meet eligibility criteria will be scheduled with research staff for a baseline assessment session. Informed consent will take place in person or via telehealth, using an IRB approved platform, such as Doxy.Me or RedCap. In a private setting apart from their partner, participants will be provided with a description of the nature and requirements of study participation, and asked to read and sign an IRB-approved consent form prior to beginning any study procedures. In the event of eConsent, the informed consent process will still take place privately. If partners do not have the ability to each have a private room for eConsent within their residence(s), separate appointments may be arranged to maintain privacy and to meet with each individual partner separately. Informed consent will be collected by, PI ([name]), or trained IRB approved personnel. All study personnel are trained in human subjects research.

Participants will also be informed that they are not required to make a decision about whether or not they choose to participate on that day. Although participants will complete the informed consent procedure apart from their partner to ensure each partner's safety and confidentiality and to minimize coercion, all participants will have the opportunity to discuss participation with their partner prior to providing informed consent. Participants who are eligible to participate and choose to do so will be encouraged to ask any questions they might have about the study. Both the participant and research staff member will sign the form.

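### The main safety reason says IPV that is severe and/or unilateral is screened out, but both exclusion lists remove only IPV that is both severe and unilateral in the past 6 months

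*Combined protocol and SAP*

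**What the plan says.** Three places in the combined protocol and SAP bear on who is kept out because of existing IPV.

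- **Human Subjects Research, 1.C Potential Risks (increased IPV).** The risk is described as very low "primarily because the study team screens out for any severe and/or unilateral IPV at the screening visit". The next sentence reads "These individuals should not participate in a clinical trial and are referred clinically". No look-back window is given.
- **Approach, Participants, exclusion criterion 8.** The exclusion is "severe and unilateral IPV in the past 6 months (for safety"; the closing words mark it as a safety criterion.
- **Human Subjects Research, 1.A, exclusion criterion 8.** The exclusion is "Severe *and* unilateral IPV in the past 6 months", with the conjunction italicised.

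On screening, the recruitment and consent text in section 2 says "The screening measure contains questions directly pertaining to the study's inclusion and exclusion criteria". On what happens after entry, section 1.C says "If the study team becomes aware of increased IPV during the trial, staff will notify the PI", and its paragraph on ecological momentary assessment (EMA) says "Participants will be informed that study staff will not receive EMA responses in real time".

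**The concern.** The risk statement and the eligibility criteria describe different screens. The statement's 'and/or' covers IPV that is severe, IPV that is unilateral, and IPV that is both. The criteria's 'and' covers only IPV that is both.

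The difference matters because the protocol itself makes this screen the main ground for its low-risk judgement. If 'and/or' is a slip, that ground claims more protection than the criteria give. If 'and/or' is intended, the lists admit couples who, by the sponsor's own account, should not take part. The text needs changing in either case.

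The entry screen also carries real weight. The response to increased IPV begins when staff learn of it, and they do not see EMA answers as they are given.

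**Working it through.** No figure in the plan depends on this point, so the check is a comparison of wording.

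**Step 1: read each rule.** The risk statement removes IPV if it is severe or unilateral or both. Criterion 8 removes it only if it is severe and unilateral, in the past 6 months. One could try to read 'severe and unilateral' as naming two separate kinds of IPV, which would remove the conflict. The Human Subjects list speaks against that reading. It italicises the 'and' in criterion 8, and it italicises the same word in inclusion criterion 4, where current alcohol use is required in addition to the diagnosis.

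**Step 2: apply both rules within the 6-month window.** Two levels of severity times two of direction give 2 × 2 = 4 types.

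| IPV in the past 6 months | Risk statement | Criterion 8 (both lists) |
|---|---|---|
| Severe, unilateral | Out | Out |
| Severe, bilateral | Out | Not excluded |
| Non-severe, unilateral | Out | Not excluded |
| Non-severe, bilateral | Not excluded | Not excluded |

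The risk statement removes 3 of 4 types and the lists remove 1 of 4. They disagree on 3 − 1 = 2 types.

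**Step 3: does another criterion close the gap?** The IPV inclusion criterion needs only one partner to report at least one instance in the past two years. It does not bar severe bilateral IPV or non-severe unilateral IPV, and no other exclusion criterion concerns IPV.

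**Step 4: does the described screening close it?** The section 2 text ties the screening measure to the listed criteria, but it describes the step before the baseline session is scheduled. It does not settle what is asked at the screening visit. Apart from the risk statement itself, no text describes a wider IPV rule.

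**Step 5: what else supports low risk?**

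- The paragraph before the risk statement cites the team's own studies and other published work. It concludes that participants' "risk of increased aggression as a direct result of study participation is extremely low".
- The Safety and Monitoring Plan provides for IPV monitoring with the Revised Conflict Tactics Scale (CTS-2) and the Time Line Follow-Back (TLFB). It also advises participants to tell staff about worsening aggression.
- The adverse event follow-up text provides for a weekly review by the PI and Study Physician.
- Against this, Table 1 schedules the CTS-2 and TLFB only at baseline and exit, and the Adverse Events Form only at exit.

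This support is independent of the entry screen, but the monitoring between baseline and exit is limited.

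**The case against.** The strongest reply is that the operative rule is not in doubt. Two lists agree on the criterion and the window, and one stresses the conjunction. On that view the risk statement is a loose paraphrase in one narrative sentence. No endpoint, analysis or power figure depends on it, and the document that contains it also contains both lists. Most of this stands, and it is why the point is graded as an inconsistency to be fixed and no higher. It does not remove the point, because the loose sentence is the one that gives the main safety reason and says who should not participate.

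A reader might infer more than the documents support:

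- **That screening would be applied inconsistently.** The two lists agree, so this is not shown.
- **That the whole low-risk judgement falls.** It has separate support, as set out in the working, and IPV that is both severe and unilateral in the past 6 months is excluded under every text.
- **That severe unilateral IPV from more than 6 months ago is a further gap.** The risk statement gives no window. It may or may not share the 6-month limit, so this is unclear and not a demonstrated conflict.
- **That half of the couples are affected.** Two of four counts types, which need not be equally common.
- **That recruitment would suffer by some stated amount.** The document gives no share of couples in the disputed types, so no such figure can be supported.
- **That the monitoring board was misinformed.** Nothing says that the board relies on this sentence.

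**Conclusion.** The point holds as an internal inconsistency that should be fixed. Within the past 6 months, severe bilateral IPV and non-severe unilateral IPV are described as screened out but are excluded by neither list. The stated main reason for very low risk is therefore delivered only in part. The size is two of four types, and the number of couples cannot be derived from the document. The conflict weakens the main reason and leaves the rest of the safety case standing.

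The conclusion rests on reading 'and' in criterion 8 as requiring both features, which the italics support, and on the absence of any other text describing a wider screen. It is not a criticism of criterion 8 as a clinical rule.

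**What to change.** The sponsor and investigator should reconcile the three places: the Participants paragraph in the Approach, exclusion criterion 8 in section 1.A, and the increased-IPV statement in section 1.C. All three should state one rule ('and' or 'and/or') and one look-back window in identical words, and the risk statement should describe the rule actually applied. The choice of rule is theirs.

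The cost is a protocol amendment through the IRB. If the lists stand, only the wording of the risk statement changes. If the wider rule is the intended one, both lists change and eligibility narrows, by an amount the document does not allow anyone to estimate. Criterion 8 names no instrument. The CTS-2 is already collected at baseline, so the sponsor should confirm whether it is enough to apply the chosen rule.

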## 2. Adequacy of Protection against Risks

Recruitment and Informed Consent Procedures. All personnel will be trained in the responsible conduct of research. Participants will be recruited from MUSC treatment clinics, community settings, and ads placed on the internet. The screening measure contains questions directly pertaining to the study's inclusion and exclusion criteria. Participants who meet eligibility criteria will be scheduled with research staff for a baseline assessment session. Informed consent will take place in person or via telehealth, using an IRB approved platform, such as Doxy.Me or RedCap. In a private setting apart from their partner, participants will be provided with a description of the nature and requirements of study participation, and asked to read and sign an IRB-approved consent form prior to beginning any study procedures. In the event of eConsent, the informed consent process will still take place privately. If partners do not have the ability to each have a private room for eConsent within their residence(s), separate appointments may be arranged to maintain privacy and to meet with each individual partner separately. Informed consent will be collected by, PI ([name]), or trained IRB approved personnel. All study personnel are trained in human subjects research.

Participants will also be informed that they are not required to make a decision about whether or not they choose to participate on that day. Although participants will complete the informed consent procedure apart from their partner to ensure each partner's safety and confidentiality and to minimize coercion, all participants will have the opportunity to discuss participation with their partner prior to providing informed consent. Participants who are eligible to participate and choose to do so will be encouraged to ask any questions they might have about the study. Both the participant and research staff member will sign the form.

The informed consent document will outline 1) the sponsorship of the study; 2) the nature, purpose and procedures of the research study; 3) the voluntary nature of participation (i.e., participation is not required and can be discontinued at any time; 4) duration of the study; 5) potential risks and discomforts and potential benefits of participating; 6) that all information will be kept confidential subject to the provisions of state and federal law; 7) compensation; and 8) alternative treatments. Participants will be informed that they can discontinue participation in the study at any time and that this decision will not influence the care they receive at any MUSC clinic (if they are existing patients of MUSC), regardless if they are located in Charleston, elsewhere in SC or outside of the state of SC.

Assessment Procedures. Some participants may experience distress in response to self-report and interview measures pertaining to alcohol use, IPV, or associated areas of functioning. Our team is equipped with standard operating procedures to conduct baseline inclusion and exclusion interviews remotely using IRB-approved telehealth web platforms such as Doxy.Me, Microsoft Teams or ZOOM. While eConsent and telehealth-based assessment has been enormously successful in [name] ongoing trials among couples with AUD due to its convenience and accessibility, some participants might determine after attempting that they prefer an in-person appointment. Participants will be informed that they are welcome to change modalities between consent, screening, and exit interview procedures. Participants may also experience physical or psychological discomfort during the study assessments at home. However, based on the research team's past experience and available literature the risks involved in the proposed project are minimal and manageable. Nevertheless, we have a specific protocol in place to manage participant distress in the event that it arises. This protocol is discussed in more detail below. We will also inform participants during the informed consent process that they may terminate study procedures at any point. Our past and ongoing research suggests that the measures and methods proposed in this study can be implemented without undue psychological distress or exacerbation of symptoms. This experience includes numerous federally-funded projects with individuals who use alcohol and drugs.

In the event that a participant becomes distressed secondary to participation, they will be encouraged to contact [name]. In addition, local participants will have access to urgent care services at MUSC treatment clinics. The study team will ensure a local urgent care clinic has been identified for participants who live outside of the Charleston area and outside of the state of South Carolina. Any adverse effects noted by any project personnel will be immediately reported to the PIs, who will then report these adverse effects in writing to the IRB and NIH per protocol (see the Data and Safety Monitoring Plan at the end of this section for more details). The

research team includes several licensed clinical psychologists and a psychiatrist who are equipped to help participants manage distress and to evaluate conditions in which participants need additional assistance. In the event that a participant becomes significantly distressed, the PI will contact the participant later that day to check-in and the following day to ensure they have received necessary resources, and to assess their safety and welfare. If called by participants, the PI will attempt to address all participant concerns and set up a referral for treatment for those who desire it.

Alcohol Withdrawal. Participants will be screened for acute alcohol withdrawal at the outset of the study. Participants reporting CIWA-Ar scores >8 will be excluded from participation and referred clinically.

Confidentiality. Several procedures that have been used previously by the research team will be followed to ensure confidentiality of all participants. Following our established procedures, all research staff are trained in the importance of maintaining confidentiality and will complete the required NIH and MUSC training in protection of human subjects. They will be informed that breach of confidentiality may result in termination of employment and will sign a pledge attesting to their commitment to maintaining subject confidentiality. All presentations of the project data will report findings in terms of groups; no individual identifying information will be presented.

During data collection, data for each participant will be linked to a unique identifier that will be assigned to each participant at the outset of the study. This identifier will be linked to identifying information via a code key until the conclusion of data collection for that participant. The code key linking identifying information to data will be kept on a password-protected computer or locked filing cabinet separate from the data within our team's locked research office. Only key study personnel will have access to this information. Participants who use rideshare services will be required to use their own phones to preserve confidentiality; they will be compensated per the receipt indicated in the scheduling of their transportation.

All computers that will store data for this project are in locked rooms when users are not present. All computers and servers are password-protected. Only individuals with a correct password can gain access to individual computers and servers. To protect individual computers from unauthorized intrusion, computer users do not have administrative privileges on workstations and servers, and therefore are unable to install unauthorized applications and services or modify critical system files that could create vulnerabilities. In addition, firewalls protect each individual computer and server from intrusion. Further, MUSC has additional firewalls and other security devices to protect the network infrastructure from outside their respective campuses. Auditing and password security policies are enabled on computers and servers to track login attempts and restrict unauthorized access.

Most data are collected electronically and all data will be stored securely and separately from identifying data. Paper consent forms will be stored in locked file cabinets in the laboratory, separate from the data. A code key which links participant names to the unique ID number and any hard copies of participants' data will be kept in separate locked filing cabinets. When each participant completes the study, the code key that links his or her identity to their data will be destroyed.

All phones and activity trackers loaned to participants for the purpose of EMA, psychophysiology, and geolocation data collection will be wiped and reset prior to re-issuing the technology to another participant. Study phones will be password-protected and participants using their own devices will be encouraged to enable password protection. Additionally, the smartphone application itself from illumivu requires user identification to complete EMA sessions.

RedCap Data Management and Security. We plan to use REDCap for data capture and management. REDCap (Research Electronic Data Capture) is a software toolset and workflow methodology for electronic collection and management of research and clinical trial data. REDCap provides secure, web-based flexible applications, including real time validation rules with automated data type and range checks at the time of entry. Exports are made available for several statistical packages including SPSS, SAS, SATA, R and Microsoft Excel. The system allows the research team to create and engage respondents using a variety of notification methods. REDCap data dictionaries can be distributed for reuse at multiple institutions. A library of data dictionaries is made available for standards-based data collection forms and validated instruments. The underlying database is hosted in a secure data center at MUSC, a secure environment for data systems and servers on campus, and includes redundancy, failover capability, backups and extensive security checks. The system has several layers

of protection including, user/group account management, "Data Access Groups" which allow data to be entered by multiple groups in one database with segmented user rights for entered data, audit trails for all changes, queries and reports, and Secure Sockets Layer (SSL) encryption.

Security of Remote Data Storage Cloud including Physiology and Geolocation. This project will use a cloud-based smartphone application provided by Ilumivu, Inc. in a fee-for-service manner to collect remote ecological momentary assessment data. We will use the same platform through Ilumivu for physiological and geolocation data collected via wearable activity trackers. Participants will be informed of the specific data points that will be collected from their particular smartphone (or study smartphone) model and the activity tracker model. Study data will not be shared outside the study team or analyzed for reasons outside the scope of this research project. In addition, the Ilumivu application system allows specific security measures including requiring a user identification and password. The core system implements a hierarchical, roles-based security model that determines access to information and system capabilities. Data files are stored in a secure database and never on the server's file system. Data can be stored in either an encrypted manner or in clear-text. Secure Sockets Layer (SSL) protocols are also implemented using the client's certificate or one acquired by Ilumivu on behalf of its user. All data are encrypted in transmission.

Safety and Monitoring Plan. A procedure for clinical deterioration has been established based upon our experience with previous and ongoing NIH-funded clinical trials. All investigators and study staff will be instructed to use their best clinical judgment regarding emergencies and inform the PI as soon as possible. In addition to relying on clinical judgment on the part of the licensed providers on this team who are experienced with this population, we will also monitor alcohol and drug use, depression, and IPV using standardized measures (TLFB, BDI-II, CTS-2, breathalyzer tests and urine drug screens) in order to detect any symptom worsening requiring further evaluation. Additionally, participants will be advised to observe any signs of worsening alcohol use, depression symptoms, or aggression, and to discuss these challenges with study staff.

Participants will be withdrawn from the study and referred for more intensive treatment if: (1) there are increases in alcohol or drug use leading to the need for a more intensive level of care (i.e., medical detoxification, inpatient or partial hospitalization); (2) there is active suicidal or homicidal ideation and/or intent; (3) there is an inability to manage the participant psychiatrically within the inclusion/exclusion criteria of the study (i.e., need for the initiation of psychotropic medications; development of psychosis); or (4) there is an inability to complete study appointments due to incarceration or hospitalization.

There is a well-established protocol at MUSC for emergency psychiatric evaluation, crisis intervention and/or psychiatric hospitalization for suicidal, homicidal, psychotic or other acutely distressed participants. Immediately on detection of these needs, the assessor/therapist will page a psychiatrist to review the participant's situation. If appropriate, the psychiatrist will personally evaluate the participant. If the participant is in the office, the participant will be escorted by a study staff member to the psychiatric walk-in clinic or emergency room. Psychiatric hospitalization is available for emergencies.

Participants will be informed during informed consent procedures of the standard limitations of confidentiality such as imminent risk of harm to self or others, or child or elder abuse. Participants will be informed that they can decide not to answer any questions and, should they become distressed or are uncomfortable with continuing to participate, they may discontinue participation at any time without penalty. The compensation schedule will be stated verbally and in writing in the initial study description and the informed consent procedure. The participant's copy of the consent form will provide contact phone numbers and email for the PIs should a participant have any questions, comments, or concerns about their participation. Participants will have the opportunity to have a copy of the consent form mailed to them at any time.

All telehealth participants (in state and out of state) complete a participant locator form with study staff, that allows the study team to identify local emergency care facilities and contact information. Specifically for out of state or remote participants, the study staff will compile a list of referrals and emergency contacts to provide to study participants ahead of enrollment.

**Suicide Specific Risk Identification and Response Plan.** Specific precautions will be taken to prevent harm to participants and potential participants. Project staff will be supervised by [name] (PI), and Drs. [name] and [name] (local Co-Is), who are licensed psychologists. All project staff will be specifically trained to assess suicide risk, including ideation, plan, and intent as well as history of ideation or attempts, and they will be trained to develop a safety contract with participants. In initial screening procedures, participants identified by clinical interview with both suicidal ideation and acute intent will be excluded from the study, but will be offered emergency psychiatric care. This care is available 24 hours per day at MUSC, as indicated above. In addition to the assessment measures specified in the Research Plan, the Beck Depression Inventory-II will be administered. Any participant any participant scoring above 25 on the BDI-II (administered at each visit) or answering a "1" or above to question 9 will be specifically queried about suicidal ideation and intent. In any instance where ideation or intent is identified, the PI will be immediately notified and will contact the participant for further evaluation. If both ideation and intent are present, the aforementioned hospital intervention will be provided. Thus, all assessment points represent suicide risk identification, assessment, and intervention opportunities. Study staff will be specifically trained regarding the increased risk of suicide in Veterans, and will receive specific instruction of suicide risk assessment, should a Veteran be enrolled.

All telehealth participants complete a participant locator form with study staff, that allows the study team to identify local emergency care facilities and contact information. Specifically, for out of state or remote participants, the study staff will compile a list of referrals and emergency contacts to provide to study participants ahead of enrollment. Ahead of appointments that are taking place outside of the Charleston area (both in SC and outside of SC), the study team will ensure a local (to participant) emergency line has been identified. In the event of a true emergency, the study team can contact the local authorities or emergency dispatch to send help to participant.

